6.1. The pre-operative Phase

During this phase, patients will be screened for fulfillment of the inclusion and exclusion. Patient's demography, history of diseases will be collected, laboratory investigations such as Hemoglobin count, Platelets count, APTT, INR, SGPT, SGOT, Serum albumin, serum Bilirubin, serum creatinine and random blood glucose and pregnancy test for females in childbearing period.

APTT should be done before IMP administration, in addition to the patient's data of Thrombexx® administration regimen decided by the treating investigator according to the standard clinical practice or as prescribed in the usual manner in accordance with the terms of the local marketing authorization with regards to dose, population and indication (and within the approved label).

Medical history and Medication history should also be collected.

Main complaint of the patient during routine physical examination should be recorded

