Title Page

A Prospective, Single- Center, Phase IV Interventional, Single Arm **T**rial for the
Evaluation of subcutaneous recombinant **H**irudin 15 mg (RB variant) in
prophylaxis of Deep Vein Thrombosis (**DVT**) post major orthopedic operations

Principle Investigator: [name]

Sub Investigator: [name]

Study Site: Alexandria University

Protocol Name: THRIVE-DVT

Protocol Number: Sub-Thromb-001

Version:1.0, amendment 1

Date: 25th of January, 2022

CONFIDENTIALITY STATEMENT

This study was performed in compliance with Good Clinical Practice (GCP), including the archiving of essential documents. This report has been prepared in accordance with ICH Harmonized Tripartite Guideline on the Structure and Content of Clinical Study Reports, dated November 1995.

Any and all information presented in this document shall be treated as confidential and shall remain the exclusive property of **Minapharm Pharmaceuticals** (or any of its affiliated companies). The use of such confidential information must be restricted to the recipients for the agreed purpose and must be disclosed, published or otherwise communicated to any unauthorized persons, for any reasons, in any form whatsoever without the prior written consent of **Minapharm Pharmaceuticals** (or the concerned affiliate company); "Affiliate Company" means any corporation, partnership or other entity which at the date of communication or afterwards with **Minapharm Pharmaceuticals**

1. Synopsis

Title	Description
Study Title	Prospective, Single- Center, Interventional, Single Arm Trial for the Evaluation of subcutaneous recombinant Hirudin 15 mg (RB variant) in prophylaxis of Deep Vein Thrombosis (DVT) post major orthopedic operations
Study number	Sub-Thromb-001
Study Phase	Phase IV
Study Design	Prospective, Single arm, single-center
Study population	Patients undergoing major orthopedic operations
Study procedures	
Drug: r-Hirudin Other Name: Thrombexx
 
100 Patients will be treated with r-Hirudin (Thrombexx) for a total of 15 days beginning with 15 mg BID s.c starting 6 hours after surgery or upon adequate hemostasis and continued until end of study.

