
Study medication
	
Thrombexx ;
 
Because thrombin plays a central role in thrombogenesis, the goal of most treatment regimens is to block thrombin generation or inhibit its activity.
 
 1- r-Hirudin binds directly with thrombin to its active & fibrinogen binding site. 2- r-hirudin does not require access to heparin binding site & can thus neutralize clot bound thrombin. Hence, down regulating thrombin generation & potentially enhancing early revascularization. 
Direct thrombin inhibitors were developed to overcome the inability of the heparin/ antithrombin complex to inactivate bound thrombin. In contrast to heparin and low-molecular-weight heparin, which catalyze the inactivation of thrombin and activated factor X (factor Xa) by antithrombin, direct thrombin inhibitors bind to thrombin and block its interaction with its substrates.
 
II- They do not bind to plasma proteins; direct thrombin inhibitors produce a more predictable anticoagulant response than heparin.
 
III- Unlike heparin, direct thrombin inhibitors do not interact with platelet factor 4 or high-molecular-weight multimers of von Willebrand factor. Consequently, the activity of direct thrombin inhibitors in the vicinity of a platelet-rich thrombus is not compromised.
 
IV- Finally, thrombin bound to fibrin or fibrin degradation products is susceptible to inactivation by direct thrombin inhibitors. Because the active site of thrombin is not involved in the interaction of the enzyme with fibrin, it remains accessible to active site-directed thrombin inhibitors. Consequently, these agents inactivate fibrin-bound thrombin without displacing the enzyme from fibrin. In contrast, bivalent thrombin inhibitors, such as Hirudin and bivalirudin, displace bound thrombin during the inhibition reaction by competing with fibrin for access to exosite 1 on thrombin.

	
Dose: In DVT Prophylaxis: 15 mg twice daily, subcutaneous for 15 days
 
In case of renal insufficiency, the dose is titrated because r-Hirudin is excreted renally. According to Creatinine clearance: •Creatinine clearance > 31-60 ml/min (5 mg s.c twice daily) •Creatinine clearance < 31 ml/min (1.7 mg s.c twice daily)

Sample size	100 patients

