6.2. The operative Phase

During this phase, patient's registries for the type of surgery done, Type of anesthesia, patient position and type of prosthesis, & blood transfusion during surgery should be recorded. And IMP dispensing 6 hours after surgery or upon adequate hemostasis will be done. APTT will be done 4 & 8 hours after the first dose

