7.2. STUDY PHASES

The study consists of 3 phases:

Visit 1: Preoperative phase (screening)

- ❖ Patient Screening (Check eligibility)
- ❖ Signed ICF
- ❖ Gathering Patient Information as Demographic, Vital Signs, BMI, Physical Examination, Medical History, Concomitant medications
- ❖ Laboratory Investigations (Hb, PLt count, APTT, INR, SGPT, SGOT, Serum Albumin, Serum Bilirubin, serum creatinine, Creatinine clearance, Random blood sugar)
- ❖ Patients main complaint (Knee, Hip)

Operative phase (Day 0)

Patient Data to be collected:

- ❖ Type , Date of surgery
- ❖ Type of anaesthesia
- ❖ Patient position
- ❖ Type of prosthesis
- ❖ Blood transfusion

Start of IMP administration.

APTT 4 & 8 hours after IMP administration

Visit 2: Post operative phase (Follow-up 1 (Day 1))

- ❖ Assessment of bleeding
- ❖ Type of blood transfusions
- ❖ Assessment of DVT
- ❖ Routine bilateral compression Doppler (confirmation for DVT)
- ❖ Assessment of PE
- ❖ Spiral CT (confirming PE)
- ❖ IMP administration
- ❖ Laboratory investigations (Hb%, Platelets count)
- ❖ APTT

Assessment will be done in the hospital, as post-operative period before discharge from hospital.

Visit 3: Follow-up 2 (Day 8)

- ❖ Assessment of bleeding
- ❖ Type of blood transfusions
- ❖ Assessment of DVT
- ❖ Routine bilateral compression Doppler (confirmation for DVT)
- ❖ Assessment of PE
- ❖ Spiral CT (confirming PE)
- ❖ IMP administration
- ❖ Laboratory investigations (Hb%, Platelets count)
- ❖ APTT

Assessment in day 8 will be done from outpatient clinic in most patients.

Visit 4: Follow-up 3/ End of Study (Day 15)

- ❖ Assessment of bleeding
- ❖ Type of blood transfusions
- ❖ Assessment of DVT
- ❖ Laboratory Investigations
- ❖ Routine bilateral compression Doppler (confirmation for DVT)
- ❖ Assessment of PE
- ❖ Spiral CT (confirming PE)
- ❖ APTT
- ❖ End of Study

Assessment in day 15 will be done from outpatient clinic.

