12. TREATMENT OF TRIAL PARTICIPANTS

12.1. Description of Study Medication(s)

Because thrombin plays a central role in thrombogenesis, the goal of most treatment regimens is to block thrombin generation or inhibit its activity.

1- r-Hirudin binds directly with thrombin to its active & fibrinogen binding site.

2- r-hirudin does not require access to heparin binding site & can thus neutralize clot bound thrombin. Hence, down regulating thrombin generation & potentially enhancing early revascularization.

Direct thrombin inhibitors were developed to overcome the inability of the heparin/antithrombin complex to inactivate bound thrombin. In contrast to heparin and low-molecular-weight heparin, which catalyze the inactivation of thrombin and activated factor X (factor Xa) by antithrombin, direct thrombin inhibitors bind to thrombin and block its interaction with its substrates.

II- They do not bind to plasma proteins, direct thrombin inhibitors produce a more predictable anticoagulant response than heparin.

III- Unlike heparin, direct thrombin inhibitors do not interact with platelet factor 4 or high-molecular-weight multimers of von Willebrand factor. Consequently, the activity of direct thrombin inhibitors in the vicinity of a platelet-rich thrombus is not compromised.

IV- Finally, thrombin bound to fibrin or fibrin degradation products is susceptible to inactivation by direct thrombin inhibitors. Because the active site of thrombin is not involved in the interaction of the enzyme with fibrin, it remains accessible to active site-directed thrombin inhibitors. Consequently, these agents inactivate fibrin-bound thrombin without displacing the enzyme from fibrin. In contrast, bivalent thrombin inhibitors, such as Hirudin and bivalirudin, displace bound thrombin during the inhibition reaction by competing with fibrin for access to exosite 1 on thrombin.

Dose of Thrombexx®:

In DVT Prophylaxis: 15 mg twice daily, subcutaneous for 15 days

In case of renal insufficiency, the dose is titrated because r-Hirudin is excreted renally.

According to Creatinine clearance:

Creatinine clearance > 31-60 ml/min (5 mg s.c twice daily)

Creatinine clearance < 31 ml/min (1.7 mg s.c twice daily)

In case of patients who will receive spinal anesthesia; Thrombexx will be given 8-10 hours before puncture/catheter and 2-4 hours after puncture/catheter manipulation or removal, as per European Guidelines.

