2.1 The Pre-Operative Phase

During this phase, patients will be screened for fulfillment of the inclusion and exclusion. Patient's demography, history of diseases will be collected, laboratory investigations such as Hemoglobin count, Platelets count, Activated Partial Thromboplastin Time (APTT), INR, SGPT, SGOT, Serum albumin, serum Bilirubin, serum creatinine and random blood glucose and pregnancy test for females in childbearing period

APTT should be done before IMP administration, in addition to the patient's data of Thrombexx® administration regimen decided by the treating investigator according to the standard clinical practice or as prescribed in the usual manner in accordance with the terms of the local marketing authorization with regards to dose, population and indication (and within the approved label).

Medical history and Medication history should also be collected.

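### As worded, the spinal-anesthesia clause in Protocol 12.1 orders a pre-operative dose, against the post-operative start set elsewhere; Protocol 6.1 and SAP 2.1 also describe a protocol-set regimen as investigator-decided and on-label

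*Protocol*

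**What the plan says.** **Start of dosing.** The synopsis has treatment "starting 6 hours after surgery or upon adequate hemostasis and continued until end of study". Protocol 6.2 and SAP 2.2 agree: "IMP dispensing 6 hours after surgery or upon adequate hemostasis will be done". Protocol 7.2 lists "Start of IMP administration" in the operative phase (Day 0), after the surgical data. The flow chart in 7.1 marks study drug on Days 0, 1, 8 and 15 and not at screening.

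**Spinal anesthesia.** One sentence at the end of Protocol 12.1 says that "Thrombexx will be given 8-10 hours before puncture/catheter and 2-4 hours after puncture/catheter manipulation or removal, as per European Guidelines". The synopsis dose text does not carry it.

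**Regimen.** The synopsis and Protocol 12.1 give "15 mg twice daily, subcutaneous for 15 days", lowered to 5 mg or 1.7 mg twice daily by creatinine clearance. Protocol 6.1 instead speaks of a "regimen decided by the treating investigator according to the standard clinical practice or as prescribed in the usual manner", in line with the local marketing authorization "with regards to dose, population and indication (and within the approved label". SAP 2.1 repeats this: "regimen decided by the treating investigator according to the standard clinical practice".

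**Label, as the documents summarize it.** Protocol 4.1 and SAP 1.1, citing a 2004 package insert, describe 15 mg given 5-15 minutes before surgery, then 15 mg twice daily for 9-12 days, with 12 days as the maximum in bedridden patients.

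**The concern.** The spinal clause is the main point. It governs an anticoagulant around neuraxial puncture and can be applied in opposite ways: give a dose 8-10 hours before the needle, or make sure that no dose has been given in that window. Only the second fits a post-operative first dose. The major-bleeding endpoint would not reliably show the harm. Its named sites are intracranial, retroperitoneal and prosthetic joint, so a spinal bleed would count only if it met the hemoglobin and transfusion criterion, and would otherwise appear only as an adverse event. The dosing rule itself therefore has to be clear.

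The regimen wording matters less. A single-arm trial reports event rates on a stated regimen. If one section sets that regimen and another calls it the treating investigator's choice under the label, it is unclear which text defines a protocol deviation.

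**Working it through.** No computed figure in the plan is at issue. The check compares texts and adds simple arithmetic.

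**A. Spinal clause against the start of dosing**

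| Place | Timing of first dose |
|---|---|
| Synopsis; Protocol 6.2; SAP 2.2 | 6 h after surgery, or when hemostasis is adequate |
| Protocol 7.1 flow chart | First mark on Day 0, none at screening |
| Protocol 7.2 | Operative phase, Day 0 |
| Protocol 12.1, spinal patients, as worded | 8-10 h before puncture |

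1. *Literal reading, dose before puncture.* Puncture for the anesthetic comes before the operation, so a dose 8-10 h earlier is pre-operative. For a puncture before 08:00 even the 8 h dose falls on the day before surgery (08:00 - 8 h = 00:00), where the flow chart has no mark.
2. *Literal reading, dose after puncture.* Assume puncture 0.25-0.5 h before incision and surgery of 1-3 h (neither is in the documents). A dose 2-4 h after puncture then falls between 2 - 0.5 - 3 = -1.5 h and 4 - 0.25 - 1 = +2.75 h relative to the end of surgery. That is always before the 6 h point, but the post-operative part of the range could comply if hemostasis is adequate. The firm contradiction is with the dose before puncture.
3. *Interval reading.* With a single puncture and no catheter, a start 6 h after surgery is more than 6 h after puncture and so clears the 4 h upper limit. A start triggered by hemostasis need not. With adequate hemostasis at the end of a 1 h operation and puncture 0.25 h before incision, the dose could come 1 + 0.25 = 1.25 h after puncture, below even the 2 h limit. The interval reading therefore also needs an explicit floor.
4. *APTT, only if pre-operative dosing is intended.* The 4 h sample would fall 8 - 4 = 4 to 10 - 4 = 6 h before puncture, and the 8 h sample 8 - 8 = 0 to 10 - 8 = 2 h before it. SAP Table 10 pools all patients. APTT change is a listed primary endpoint (Protocol 8.1, SAP 4.1) but not a primary analysis variable (Protocol 17.2.1, SAP 8.2.1).

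**B. Protocol regimen against the label summary (full dose)**

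| | Trial | Label summary, upper end |
|---|---|---|
| First dose | after surgery | 5-15 min before surgery |
| Days of twice-daily dosing | 15 | 12 |
| Injections | 15 x 2 = 30 | 1 + 12 x 2 = 25 |
| Total | 30 x 15 = 450 mg | 25 x 15 = 375 mg |

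Difference: 15 - 12 = 3 days; 30 - 25 = 5 injections (5/25 = 20%), or 75 mg. The unit dose and frequency, 15 mg twice daily, agree. Start and duration do not, and nothing in either document reconciles them.

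**The case against.** *On the spinal clause.* The reference to European guidelines and the mention of catheter manipulation or removal point to minimum intervals. On that reading no pre-operative dose is given and the APTT samples stay where they were planned. This largely stands as a view of intent. A reader might infer that spinal patients will get a dose before surgery, or that the APTT endpoint is already compromised. The documents do not support either conclusion, because both need the literal reading, which the clause's own context disfavors. What remains is that the clause is phrased as an instruction to dose, and no other text corrects it.

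*On the regimen.* The sentence in Protocol 6.1 sits in the screening section and concerns data to be collected. It names dose, population and indication, and the 15 mg dose does match. The trial does not use one dose for everyone: renal function sets three levels, the start depends partly on a judgment of hemostasis, and Protocol 5.2 and SAP 3.2 list dose and duration among the predictive factors. All of this is fair, and it makes the point minor. But renal adjustment is a protocol rule, and duration can vary through early stopping without being the investigator's choice. The closing parenthesis on the label is also wider than dose, population and indication.

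A reader might infer off-label treatment. The documents do not show it: the label in force is not included, and the summary rests on a 2004 insert.

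**Conclusion.** The concern holds in two parts of unequal weight.

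1. **Spinal clause (should be fixed).** As worded, Protocol 12.1 orders a dose 8-10 h before puncture, which contradicts the post-operative start in the synopsis, Protocol 6.2 and SAP 2.2. Read as minimum intervals the contradiction disappears, but a start triggered by hemostasis could still fall inside the 2-4 h window after puncture. The share of spinal patients, and any effect on thrombosis or bleeding rates, cannot be computed from the documents. The shift in APTT timing arises only if pre-operative dosing is really meant.
2. **Regimen wording (minor).** Calling the regimen investigator-decided conflicts with a regimen set by the protocol, whatever the label says. The on-label statement conflicts with the documents' own label summary on start (before against after surgery) and on duration (15 against at most 12 days). That rests on the summary being a correct account of the label.

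**What to change.** 1. **Reword the spinal clause in Protocol 12.1**, for example: *The first dose follows 6 hours after the operation or once hemostasis is adequate, also after spinal anesthesia, but not sooner than Y hours after puncture or catheter removal. Any later puncture, or catheter manipulation or removal, takes place at least X hours after the last dose, and the next dose is given at least Y hours after it.* The sponsor sets one X from 8-10 and one Y from 2-4 using the guideline it cites, on safety grounds and not by what suits a twice-daily schedule.
2. **Only if pre-operative dosing is intended:** state it in the synopsis, Protocol 6.2 and SAP 2.2, and show APTT in SAP Table 10 by type of anesthesia, which is already collected (Protocol 6.2 and 7.2, SAP Table 7).
3. **Replace the regimen wording in Protocol 6.1 and SAP 2.1** with: *The regimen is that of Protocol section 12.1, including renal dose adjustment.* The SAP must name the Protocol, since it has no section 12.1 of its own. Either delete the on-label statement or say openly that start and duration depart from the summary in Protocol 4.1.

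Cost: wording changes in one amendment, approved by the IRB/IEC under Protocol 15.2. No extra patients or procedures are needed. Recording the time of the first dose and the date of the last would help, but neither is listed as collected, so that would be a small addition to the case report form.

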6.2. The operative Phase

During this phase, patient's registries for the type of surgery done, Type of anesthesia, patient position and type of prosthesis, & blood transfusion during surgery should be recorded. And IMP dispensing 6 hours after surgery or upon adequate hemostasis will be done. APTT will be done 4 & 8 hours after the first dose

6.3. The Follow-up Phase

During this phase, which is approximately 15 days, PE which is confirmed by spiral CT chest, any new DVT appears also to be confirmed by Doppler ultrasound, Bleeding assessment, APTT will be done on days 1, 8 & 15, concomitant medications, Hospital stay and any adverse event data will all be recorded

7. FLOW CHARTS:

7.1. STUDY FLOW CHARTS:

Activity	Pre-operative phase (Screening)	Operative phase (Day 0)	Follow-up 1 (Day 1)	Follow-up 2 (Day 8)	Follow-up 3/ End of Study (Day 15)
ICF Signature	×				
Inclusion/Exclusion Criteria	×				
Demographic Data	×				
Medical History	×				
Vital signs	×				
Concomitant Medication	×				
Physical Examination	×				

Laboratory investigation	×		×	×	×
Type of surgery		×			
Assessment of bleeding		×	×	×	
IMP Administration		×	×	×	×
Assessment of DVT			×	×	×
Assessment of PE			×	×	×
Assessment of therapeutic response					×
APTT	×	×	×	×	×
Adverse Event		×	×	×	×
Study completion					×

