Clinical & laboratory investigations	
For Events of Deep Vein Thrombosis (DVT) within 15 days post-op.)
 
All of the patients underwent Routine bilateral compression Doppler.
 
For Clinical PE (Pulmonary Embolism) Events from Day of surgery and During Hospitalization period or end of study
 
Clinical PE events PE (Pulmonary Embolism) events were confirmed by spiral CT.
 
For follow up:
 
APTT should be done before the first dose then after 4 & 8 hours of the first dose, then on days 1,8,15 post operatively.

Study duration	
Enrolment period: 3 months duration
 
Follow-up duration: Follow-up per patient will be for a period of 15 days

Eligibility Criteria	
Inclusion Criteria:
 
 18 years of age or older Body Weight >60 kg Patients undergoing major orthopedic operations

	
Patients ready to sign informed consent form (ICF) Patients should discontinue any agents that affect haemostasis prior to the study medication use unless strictly indicated. These agents include medications such as: anticoagulants, thrombolytics, non-steroidal anti-inflammatory agents (including Ketorolac tromethamine), preparations containing aspirin, systemic salicylates, ticlopidine, dextran 40, clopidogrel, other anti-platelet agents including glycoprotein IIb/IIIa antagonists or systemic glucocorticoids.
 
Exclusion Criteria:
 
Significant bleeding injury such as solid organ laceration or intracranial bleed at discretion of attending physician Hypersensitivity to Hirudin or prior documented Allergy to its components Pregnant or breast feeding Hemorrhagic stroke in preceding 3 months abnormal baseline coagulation characterized by an INR >1.4, obtained at the discretion of the treating clinician Required therapeutic anticoagulation for atrial fibrillation, prior VTE, or mechanical heart valve Patients with a history of coagulation disorder Treatment with concomitant anti-platelet agent other than aspirin 326 mg or more daily (Platelet count < 100 X10⁹ /dl) Active bleeding Subjects with a life expectancy less than 1 month

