8. STUDY OUTCOME MEASURES

8.1. Primary Endpoints

Primary end points included new onset symptomatic thrombosis requiring medical or surgical intervention or death due to thrombosis defined as fatal PE, ischemic

Sponsor: Minapharm Pharmaceuticals
Protocol Number: Sub-Thromb-001
Version: 1 amendment 1

stroke, mesenteric thrombosis, or myocardial infarction.

The number of clinical PE events will be measured by spiral CT

Mean changes in APTT where it will be done before first dose, 4 & 8 hours after first dose then on days 1,8,15 post operatively

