17. STATISTICAL METHODOLOGY

17.1. Determination of Sample Size

Sample size: Records for 100 patients who underwent major orthopedic surgery collected from 1 site

The sample size is based on literature review for previous studies, and a sample of 168 patients will be sufficient to detect an incidence of 12.5% of DVT with an acceptable error of 5%, and a 95% confidence level

17.2. Analysis Variables:

17.2.1. Primary analysis variables:

Proportion of patients experienced new onset symptomatic thrombosis
The number of clinical PE (Pulmonary Embolism) events will be measured by spiral CT

17.2.2. Secondary analysis variables:

Number of adverse events recorded
Proportion of patients experienced major bleeding

17.2.3. Statistical Method:

Descriptive analysis:

All statistical tests used a significance level of $P=0.05$, two tailed tests were performed for all analyses used statistical testing.

Descriptive analysis for quantitative data will include count, mean with 95% CI, standard deviation, median, minimum and maximum. For qualitative categorical variables; frequency and percentage and 95% confidence interval will be applied.

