9.2 Primary End Point

Table 8 *Proportion of patients experienced new onset symptomatic thrombosis*

		Follow-up 1 (Day 1)	Follow-up 2 (Day 8)	Follow-up 3/ End of Study (Day 15)	p-value
Was a Routine bilateral compression Doppler done?	Yes, N (%)				
	No, N (%)				
If “No”, please indicate a reason	Reason 1, N (%)				
	Reason 2, N (%)				
	Reason 3, N (%)				
Is the report interpreted, signed & dated by the PI or any of the designated site staff?	(Yes), N (%)				
	(No), N (%)				
If “No”, please indicate a reason:	Reason 1, N (%)				
	Reason 2, N (%)				
	Reason 3, N (%)				
If “Yes”, the report interpretation shows that the subject is:	Normal, N (%)				
	Abnormal, N (%)				
If abnormal, please state the reason:	Reason 1, N (%)				
	Reason 2, N (%)				
	Reason 3, N (%)				

Table 9 *The number of clinical PE (Pulmonary Embolism) events will be measured by spiral CT*

		Follow-up 1 (Day 1)	Follow-up 2 (Day 8)	Follow-up 3/ End of Study (Day 15)	p-value
Was a Spiral CT done?	Yes, N (%)				
	No, N (%)				
If “No”, please indicate a reason	Reason 1, N (%)				
	Reason 2, N (%)				
	Reason 3, N (%)				
Is the report interpreted, signed & dated by the PI or any of the designated site staff?	(Yes), N (%)				
	(No), N (%)				
If “No”, please indicate a reason:	Reason 1, N (%)				
	Reason 2, N (%)				
	Reason 3, N (%)				
If “Yes”, the report interpretation shows that the subject is:	Normal, N (%)				
	Abnormal, N (%)				
If abnormal, please state the reason:	Reason 1, N (%)				
	Reason 2, N (%)				
	Reason 3, N (%)				

Table 10 *Mean changes in Activated Partial Thromboplastin Time (APTT) where it will be done before first dose, 4 & 8 hours after first dose then on days 1,8,15 post operatively*

		Before 1 st dose	After 1 st dose		Post-operative			p- value
			4 h	8 h	Day 1	Day 8	Day 15	
Was an APTT test performed?	Yes, N (%)							
	No, N (%)							
If “No”, please indicate a reason	Reason 1, N (%)							
	Reason 2, N (%)							
	Reason 3, N (%)							
If “Yes”, the test result is	APTT; Mean ± SD (sec)							
APTT, % change								
p-value								
The test interpretation shows that the subject is:	Normal, N (%)							
	Abnormal, N (%)							
If abnormal, please state the reason:	Reason 1, N (%)							
	Reason 2, N (%)							
	Reason 3, N (%)							

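### The documents give no single rule for who gets a Doppler, while SAP Table 8 reports the symptomatic primary endpoint as normal or abnormal Doppler findings

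*Protocol*

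**What the plan says.** **On who is scanned.**
- Protocol synopsis, clinical and laboratory investigations: "All of the patients underwent Routine bilateral compression Doppler". No days are given.
- Protocol 7.2, follow-up visits at Days 1, 8 and 15: "Routine bilateral compression Doppler (confirmation for DVT" (the bracket closes there).
- Protocol 6.3, repeated in SAP 2.3: "any new DVT appears also to be confirmed by Doppler ultrasound".
- Flow chart 7.1: a row for "Assessment of DVT" is marked at Days 1, 8 and 15. No row names Doppler.

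**On what is counted.**
- Protocol 8.1 and SAP 4.1 define the first primary endpoint as "new onset symptomatic thrombosis requiring medical or surgical intervention or death due to thrombosis".
- Protocol 17.2.1 and SAP 8.2.1 make the analysis variable "Proportion of patients experienced new onset symptomatic thrombosis".
- SAP Table 8 takes that variable as its title. At each of the three visits it asks "Was a Routine bilateral compression Doppler done", with a reason if not, then whether the report is signed, then normal or abnormal, then the reason if abnormal. It has no row for symptoms or for intervention.

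**The concern.** Two ascertainment rules are compatible with the text. Under one, every patient is scanned on fixed days whatever the symptoms. Under the other, a scan follows when a DVT is suspected. The first finds clots that never cause symptoms and the second does not look for them.

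For an endpoint defined by symptoms this need not matter much, provided the analysis counts only symptomatic events. As laid out, Table 8 does not. The figure reported under the primary title would be the share of patients with an abnormal scan, and that share depends on the scan rule. With no control arm the effect does not cancel. If practice varied between patients or visits, the reported proportion would correspond to neither rule.

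**Working it through.** **1. Does the wording settle the rule?**

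| Place | Points to |
|---|---|
| Synopsis | Routine, all patients |
| Protocol 7.2 | Routine by its first word, confirmatory by its bracket |
| SAP Table 8 | Routine by its question, asked at Days 1, 8 and 15 |
| Protocol 6.3 and SAP 2.3 | Confirmation of a DVT that has appeared |
| Flow chart 7.1 | Days of DVT assessment, method not named |

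The listing in 7.2 does not by itself mean every patient. Spiral CT is listed at the same three visits in the same format, yet the synopsis uses CT to confirm clinical PE events. SAP Table 9 (CT) also follows the same template as Table 8. What separates Doppler from CT is the word *routine* and the synopsis statement about all patients. The sentence in 6.3 pulls the other way, because its *also* places Doppler alongside CT as a confirmatory test.

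**2. Direction.** Assume that a patient with signs is scanned under either rule. The patients scanned on suspicion are then a subset of those scanned when everyone is scanned, so scanning on suspicion cannot find more DVT.

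**3. The plan's own figure.** Protocol 17.1 says 168 patients are "sufficient to detect an incidence of 12.5% of DVT" with 5% error and 95% confidence. With n = z²p(1−p)/d²:

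1.96² × 0.125 × 0.875 / 0.05² = 168.07

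The 168 reproduces. The text does not say whether 12.5% is a rate with everyone scanned or a symptomatic rate.

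**4. Size, by assumption only.** Suppose 12.5% is the rate with everyone scanned, and let f be the share of those DVTs that would present clinically. The documents give no value for f, so it is varied. With 100 patients, expected events = 100 × 0.125 × f, and the chance of no event = (1 − 0.125f)^100.

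| f | Expected events | Chance of none |
|---|---|---|
| 100% | 12.5 | below 0.1% |
| 75% | 9.4 | below 0.1% |
| 50% | 6.25 | 0.2% |
| 25% | 3.1 | 4% |
| 10% | 1.25 | 28% |

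Exact (Clopper–Pearson) 95% intervals show what a reader would see. For 12 of 100 the interval is 6.4% to 20.0%, for 3 of 100 it is 0.6% to 8.5%, and for 1 of 100 it is 0.03% to 5.4%. The first and last do not overlap.

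**The case against.** The strongest reply is that the passages are compatible. Protocol 6.3 names a diagnostic method and does not say *only* or *if suspected*. A routine scan also confirms a DVT, which would explain the bracket in 7.2. The synopsis says all patients, and 7.2 supplies the days it omits. This stands: routine scanning is the better-supported reading. It is not the only one the wording allows, for the reasons in step 1 of the working.

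A second reply is that an asymptomatic finding is not a primary event under the written definition, however many scans are done. That is right about the definition, but Table 8 does not apply it. The scan rule could matter even with a corrected table: the synopsis lists DVT among the stopping rules, so a clot found by a scheduled scan may change the patient's later course.

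A reader might infer several stronger things that the documents do not support:
- *That flow chart 7.1 contradicts 7.2.* It does not. It omits spiral CT as well as Doppler and marks DVT assessment on the same days.
- *That a patient without symptoms may equally have no scan, one scan or three.* A single scan is a weak reading, because 7.2 supplies the days missing from the synopsis.
- *That the two studies in Protocol 4.2 show the effect of scanning.* One reports 13 of 174 (7.5%) with DVT and the other no symptomatic thrombosis. The protocol does not say how thrombosis was detected in either, so the contrast is not evidence of size.
- *That the result will miss the 12.5% planning figure because of the scan rule.* The basis of that figure is not stated.
- *That sites will differ.* There is one site, so the risk is variation between patients or visits.

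**Conclusion.** The point holds as a gap in the ascertainment rule combined with a mismatch between the primary endpoint and the table that reports it. The documents lean towards routine scanning without stating it consistently. Under that reading, Table 8 as drafted would count asymptomatic DVT under a symptomatic title. Under scanning on suspicion it would not.

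The direction is certain, given that patients with signs are scanned under both rules. The size cannot be taken from the documents. The range of 12.5 down to 1.25 expected events per 100 rests on two assumptions: that 12.5% is the rate with everyone scanned, and that between 100% and 10% of those DVTs would present clinically. It shows that the effect could be large, not that it is.

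The correction should be made because it is cheap and fixes what the primary proportion means.

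**What to change.** 1. Reconcile the synopsis, Protocol 6.3, Protocol 7.2 and SAP 2.3 to one statement: either Doppler is scheduled for every patient at Days 1, 8 and 15, or it is triggered by signs. The *routine* wording in the synopsis, 7.2 and Table 8 points to scheduled. The sponsor and investigator should confirm which was meant.
2. Show the chosen rule in flow chart 7.1 with a Doppler row.
3. In SAP Table 8, report symptomatic DVT requiring intervention, which is the primary event, separately from asymptomatic DVT found only by Doppler.
4. Record on the CRF, for each scan, what triggered it or whether symptoms were present, so that the split can be made.

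The cost is wording, one flow-chart row and one CRF and table field. The primary count may also be lower than the count of all abnormal scans. If the site has been working to the triggered reading, moving to scheduled scans would add up to 3 × 100 = 300 scans, so the choice should be made explicitly.
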